# 7.3 12-Lead Electrocardiograms

Standard 12-lead (with a 10-second rhythm strip) tracing will be used for all ECGs. All subjects will require triplicate 12-lead ECG measurement with tracings approximately one-minute apart which will be performed according to the Schedule of Events. The parameters to be recorded are QT, QTc, PR, and QRS. All ECGs should be conducted pre-dose and Fridericia's formula will be used for all QT correction calculations. The mean QTcF from these ECGs should be recorded.

# 7.4 Efficacy Assessments

# 7.4.1 Disease Assessment

Disease assessments will include complete blood count with differential, CT scans of the neck, chest, abdomen, and pelvis, peripheral blood immunophenotyping, and bone marrow biopsy and aspirate at the time points indicated on the Schedule of Events.

# 7.4.2 Disease Assessment Algorithm

All patients should have a CT scan of the neck, chest, abdomen, and pelvis with IV contrast at the time of screening or up to 28 days prior to C1D1. CTs are required at C4D1 (± 7 days). Should this CT show that the patient has achieved an iwCLL 2018 defined complete remission (CR) and absolute lymphocyte count is <4000, then a bone marrow biopsy should be performed to confirm CR.

At any other study time point beyond C4D1 excluding end of treatment, the patient may have a disease assessment if the subject achieves hematologic recovery or the treating physician suspects the patient has achieved a CR as per the 2018 iwCLL criteria. At that time, a peripheral blood immunophenotype should be ordered. If the peripheral blood

immunophenotype shows no evidence of circulating CLL cells, then CTs of the neck, chest, abdomen, and pelvis should be performed. Should the CT also confirm CR, then a bone marrow biopsy should be performed to confirm CR. The study team has 28 days to complete all necessary testing required to confirm a CR from the time a CR is suspected by the treating physician. During this time, protocol treatment may continue as prescribed.

# 7.4.3 End of Treatment Assessment

Patients who come off study for any reason should have an end of treatment assessment as outlined in the Schedule of Events.

# 7.4.4 Patients with Iodine Contrast Allergy

If a patient has a history of an allergy to iodine contrast as required by the CTs, then premedications should be offered to the patient. Premedications can follow institutional guidelines or the offered schedule below:

- 13 hours prior to CT: 50 mg PO prednisone
- 7 hours prior to CT: 50 mg PO prednisone
- 1 hour prior to CT: 50 mg PO prednisone and 50 mg PO Benadryl

If a patient refuses iodine contrast allergy even when premedications are offered, then CTs may be performed without iodine contrast.

# 7.4.5 Peripheral Blood Immunophenotyping

Peripheral blood immunophenotyping are required at screening and to confirm a CR as outlined on the Schedule of Events. This is a flow cytometry based test to confirm markers present on CLL cells. These markers include but are not limited to CD5, CD10, CD19, CD20, CD23, CD200 and kappa/lambda light chain restriction. The percentage of CLL cells that make up the total population of leukocytes should be recorded. The peripheral blood immunophenotyping must be confirmed by a CLIA approved test.

# 7.4.6 Bone Marrow Biopsy

At a minimum, marrow core and aspirate testing should include pathological review of the core sample, leukocyte and lymphocyte flow cytometry and minimal residual disease testing by flow cytometry (as per institutional standard). Other testing is at the discretion of the treating provider. The CLL FISH and CLL NGS required at the time of screening may be performed on either peripheral blood or bone marrow biopsy as long as the test produces a successful result. If the presence of lymphoid nodules are noted by the pathologist, immunohistochemistry of these nodules should be performed to define whether these are primarily T cells, B cells other than CLL cells or CLL cells. The following data points should be recorded in the corresponding eCRF.

- Lymphocyte percentage and count
- Presence of lymphoid of nodules If presence is noted, additional immunohistochemistry tests should be performed on these nodules to define whether these nodules comprise primarily T cells, B cells other than CLL cells or CLL cells

- Percent cellularity
- Percent of CLL cells detected on flow cytometry
- Percent of CLL cells comprising the entire marrow if detected by morphology and immunohistochemistry
- CLL MRD by flow cytometry (if performed)
- CLL MRD by NGS (if performed and resulted)
- Bone marrow fibrosis grade (if performed)
- Any NGS identified mutations (if performed)
- Cytogenetics (if performed)
- CLL FISH (if performed)

If the patient has had a previous bone marrow biopsy that has demonstrated a CR while on trial, a repeat bone marrow biopsy is not required while the subject is still enrolled on trial unless the treating provider suspects progression of disease.

# 7.5 Definition of Response and Progression

Disease response assessments will be according to the 2018 iwCLL definitions of response and progression. It is summarized in Table 17.

Parameter	Complete remission (CR)*	Partial remission (PR)*	Progressive disease ( PD)*	Stable disease (SD)*
	All criteria below must be met	At least 2 of the parameters of group A and 1 parameter of group B must improve if previously abnormal; if only 1 parameter of both groups A and B is abnormal before therapy, only 1 must improve	At least 1 of the criteria of group A or group B must be met; constitutional symptoms alone do not define PD	All of the criteria must be met
Group A				

Table 17. Response definitions and criteria.

Parameter	Complete remission (CR)*	Partial remission (PR)*	Progressive disease ( PD)*	Stable disease (SD)*
Lymph nodes	None > 1.5 cm	Decrease ≥ 50% (from baseline)*	Increase ≥ 50% from best response	Change of -49% to +49% from baseline
Liver and/or spleen size**	Spleen size < 13; liver size normal	Decrease ≥ 50% (from baseline)	Increase ≥ 50% from best response	Change of -49% to +49% from baseline
Constitutional Symptoms	None	Any	Any	Any
Circulating lymphocyte count	Normal	Decrease ≥ 50% (from baseline)	Increase ≥ 50% over baseline	Change of -49% to +49% from baseline
Group B				
Platelet count	≥ 100,000/mcL	> 100,000/mcL or increase ≥ 50% over baseline	Decrease of ≥ 50% from baseline secondary to CLL	Change of -49% to +49% from baseline
Hemoglobin	≥ 11.0 g/dL	> 11 g/dL or increase ≥ 50% over baseline	Decrease of > 2 g/dL from baseline secondary to CLL	Increase < 11.0 g/dL or <50% over baseline, or decrease < 2 g/dL
Marrow	Normocellular, no CLL cells, no B- lymnphoid nodules	Presence of CLL cells or of B-lymphoid nodules, or not done	Increase of CLL cells by ≥50% on successive biopsies	No change in marrow infiltrate

# 7.5.1 Complete Remission

CR requires all of the following criteria:

- Peripheral blood lymphocytes (evaluated by blood and differential count) below 4 x 10^9/L (4,000/mm^3).
- Absence of significant lymphadenopathy (i.e., lymph nodes >1.5 cm in diameter) and hepatosplenomegaly by physical examination.
- CT scan of the abdomen, pelvis, and thorax should be performed, showing no lymph nodes larger than 1.5 cm in diameter and no hepatosplenomegaly with spleen size <13cm.
- Absence of disease-related constitutional symptoms.
- Blood counts above the following values:

- Neutrophils  $\geq$ 1.5 x 10^9/L (1,500/mm^3).
- Platelets ≥100 x 10^9/L (100,000/mm^3).
- Hemoglobin  $\geq$ 110 g/L (11.0 g/dL) without red blood cell transfusion.
- Bone Marrow Aspirate/Biopsy:
  - For a CR, the cytological or pathological evaluation of the bone marrow smear or biopsy must be at least normocellular for age, without evidence for typical CLL lymphocytes by morphological criteria.
  - If the marrow is hypocellular, a repeat determination should be performed after 4 weeks, when peripheral blood counts have recovered. However, this time interval should not exceed 6 months after the last treatment. A marrow biopsy should be compared with that of pretreatment marrow.
  - The quality of the CR should be assessed for MRD by flow

For patients who fulfill the criteria for a CR, but have a persistent anemia, thrombocytopenia or neutropenia apparently unrelated to CLL, but related to drug toxicity, these patients should be labeled as a CR with incomplete marrow recovery (CRi). A bone marrow evaluation must be performed with scrutiny and not show any clonal disease infiltrate.

# 7.5.2 Partial Remission (PR)

PR is defined by achieving at least 2 of the criteria described in Sections 7.4.1a, 7.4.1b, or 7.4.1c (if abnormal before therapy), as well as one or more of the features listed in section 7.2d. If only 1 parameter in Sections 7.4.1a, 7.4.1b, 7.4.1c, 7.4.1d were abnormal before therapy, only 1 needs to improve.

- A decrease in the number of blood lymphocytes to 50% or less from the value recorded immediately prior to initial dose of therapy.
- Reduction in lymphadenopathy compared with baseline by palpation as defined by the following: (Additional assessment of response by CT scan of abdomen, pelvis, and thorax should be performed per study calendar.):
  - A decrease in lymph node size by 50% or more either in the sum of the longest diameters of the enlarged lymph node(s) selected at baseline as assessed by physical examination (an established number has been a maximum of 6) or the sum products of the same enlarged lymph nodes selected at baseline as assessed by imaging (an established number in clinical trials of lymph nodes has been up to 6).
  - No increase in any lymph node, and no new enlarged lymph node. In small lymph nodes (longest diameter < 1.5 cm), an increase <25% is not considered significant.
- A regression ≥ 50% of the extent of enlargement of the spleen below the costal margin defined by palpation, or normalization in size. When assessed by CT, scan spleen size

must have regressed by  $\geq$  50% in length beyond normal. A persistence of splenomegaly posttherapy may have limited influence on outcome in CLL.

- A regression of ≥ 50% of the extent of enlargement of the liver below the costal margin defined by palpation, or normalization in size. Given the impact of numerous medical conditions, liver size by physical examination or CT scan is not a reliable measure of hepatic involvement by CLL and should only be counted if hepatomegaly is clearly attributable to lymphoid involvement.
- The blood count should show one of the following results:
  - Platelet counts greater than 100 × 109/L (100,000/mcL) or 50% improvement over baseline.
  - Hemoglobin greater than 110 g/L (11.0 g/dL) or 50% improvement over baseline without requiring red blood cell transfusions

Patients who achieve a CR as per section 7.5.1 but bone marrow examination shows residual lymphoid nodules deemed related to CLL residual disease will be labeled as having achieved a nodular partial remission (nPR).

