### 6.6.3 Hematologic and Infectious Toxicities

Optimal supportive care should be offered to the patient in order to mitigate toxicities. Where appropriate, this includes administration of G-CSF, GM-CSF and blood/platelet transfusions as per institutional guidelines. At the start of each cycle, hold therapy until ANC  $\geq$ 500/mm^3 and platelet count is  $\geq$ 25,000/mm^3. Lymphopenia is an expected toxicity of CLL treatments and therefore should be graded and recorded as per CTCAE v5.0, but treatment holds and dose changes are not needed.

This study will utilize the 2018 IWCLL grading scale for hematologic adverse events in patients with baseline platelet count <100,000/mm^3 and/or baseline hemoglobin less than the lower limit of normal. Grading of ANC is at the nadir within the cycle, and patients who have an ANC <1 x  $10^{9}$ /L before therapy will not be evaluable for toxicity. These criteria account for baseline cytopenias secondary to CLL and are detailed in Table 12 below.

Grade	Decrease in platelets or hemoglobin from baseline value, %	Absolute neutrophil count* (nadir) x 10  /L
0	No change to 10	≥2
1	11-24	≥1 and <2
2	25-49	≥1 and <1
3	50-74	≥0.5 and <1
4	≥75	<0.5

Table 12. iwCLL Hematologic Grading

\*If the absolute neutrophil count (ANC) reaches  $<1 \times 10^{9}$ /L, it should be judged to be grade 3 toxicity. Other decreases in the white blood cell count or in circulating granulocytes are not to be considered because a decrease in the white blood cell count is a desired therapeutic end point. A gradual decrease in granulocytes is not a reliable index in CLL for stepwise grading of toxicity. If the ANC was  $<1 \times 10^{9}$ /L before therapy, the patient is not evaluable for toxicity referable to the ANC. The use of G-CSF is irrelevant for the grading of toxicity, but should be documented.

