Grade 3	Hold until platelets ∫ ≥50,000/mm  . At first occurrence, no change in dose or dosing schedule. If toxicity recurs, follow reductions in dosing schedule and drug dosages as per sections 6.6.1 and 6.6.2.	Hold until platelets J ≥50,000/mm  . At first occurrence, no change in dose or dosing schedule. If toxicity recurs, follow reductions in dosing schedule and olaparib dosages as per sections 6.6.1 and	

		decreased for the same toxicity.
Grade 4	Same management as grade 3	Same management as grade 3
	0 -	

∫Only for patients with baseline platelets ≥100,000/mm^3. For patients with baseline platelets <100,000/mm^3, hold until platelets have recovered to at least 50% of baseline value.

Event Name	Neutropenic Fever	
Grade of Event	Management/Next Dose for RP - 3500	Management/Next Dose for Olaparib
Grade 3	Hold until resolution of toxicity. G- CSF administration required. At first occurrence, no change in dose or dosing schedule. If toxicity recurs, follow reductions in dosing schedule and drug dosages as per sections 6.6.1 and 6.6.2.	Hold until resolution of toxicity. G- CSF administration required. At first occurrence, no change in dose or dosing schedule. If toxicity recurs, follow reductions in dosing schedule and olaparib dosages as per sections 6.6.1 and 6.6.2 if RP-3500 dosage already decreased for the same toxicity.

Grade 4	Hold until resolution of toxicity. G- CSF administration required. Follow reductions in dosing schedule and olaparib dosages as per sections 6.6.1 and 6.6.2.	Hold until resolution of toxicity . G- CSF administration required. Follow reductions in dosing schedule and olaparib dosages as per sections 6.6.1 and 6.6.2.if RP- 3500 dosage already decreased for the same toxicity.
Event Name	Ane	mia
Treat per institutional guidelines including blood transfusions and/or erythropoietins. Consider transfusing for symptoms with hemoglobin >8 g/dL (Grade <3) or for any Grade 3 (hemoglobin		

transfusing for symptoms with hemoglobin >8 g/dL (Grade <3) or for any Grade 3 (hemoglobin <8 g/dL). If possible, maintain RP-3500 and olaparib doses as long as patient is clinically stable, but if a dose reduction or interruption is desired, consult with the Medical Monitor.

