# 6.7 Concomitant Medications and Therapies

All administered concomitant medications (including herbal supplements) and non-medicinal therapies (including transfusions) used 28 days prior to Cycle One Day One, and until 30 days after the last dose of study therapy will be recorded in the subject's research chart and corresponding eCRF. All medications, including those used to treat adverse events, chronic conditions or diseases, or as supportive therapy should be documented in the eCRF.

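### The PR blood-count rule excludes red-cell-transfused hemoglobin but not transfused platelets or erythropoietin-supported hemoglobin, so a supported count can be scored as a response in the primary ORR

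*Combined protocol and SAP*

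**What the plan says.** - **PR, Section 7.5.2.** "The blood count should show one of the following results": for platelets, "Platelet counts greater than 100 × 109/L (100,000/mcL) or 50% improvement over baseline"; for hemoglobin, "Hemoglobin greater than 110 g/L (11.0 g/dL) or 50% improvement over baseline without requiring red blood cell transfusions". Neutrophils are not listed.
- **CR, Section 7.5.1.** Hemoglobin must reach "110 g/L (11.0 g/dL) without red blood cell transfusion". The platelet and neutrophil thresholds carry no such condition. A patient otherwise in CR whose cytopenia is put down to drug toxicity is labelled CRi.
- **Table 17.** The hemoglobin and platelet rows give thresholds only, with no transfusion or growth-factor condition. PR requires two group A improvements and one in group B, or a single improvement if only one parameter was abnormal before therapy.
- **Supportive care, Section 6.6.3.** Where appropriate, "this includes administration of G-CSF, GM-CSF and blood/platelet transfusions as per institutional guidelines". For anemia, Table 13 says "Treat per institutional guidelines including blood transfusions and/or erythropoietins".
- **Endpoint, Sections 2.1.2, 9.1.1 and 9.4.2.** ORR counts CR, CRi, PR and nPR alike. It is reported with an exact one-sided 95% interval on 24 patients and without a hypothesis test. The target is 60%.

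**The concern.** The hemoglobin condition shows that the authors did not want a transfused count read as recovery. The same reasoning applies to the platelet line beside it and to hemoglobin raised by erythropoietin, but the text covers neither. No transfusion-free or growth-factor-free period before assessment is stated. The endpoint speaks of confirmed responses, but no confirmation interval for PR is given that would screen out a short-lived transfusion effect.

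At stake is the phase II primary estimate. In a single-arm trial no control arm would share the error. Sites may also classify the same patient differently: one working from Table 17 could accept even a red-cell-transfused hemoglobin, which Section 7.5.2 rules out.

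**Working it through.** **1. The plan's own figures.** Inputs: n = 24 and the Clopper-Pearson one-sided 95% bound (Section 9.1.1). For x responders the lower bound is the 0.05 quantile of Beta(x, n − x + 1). For x = 10 to 18 this gives 24.64, 28.24, 31.94, 35.76, 39.68, 43.71, 47.86, 52.13 and 56.53%. All nine bounds in Table 19 agree once these are cut to whole percent.

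**2. Effect per patient.** One patient is 1/24 = 4.2 points of ORR. The number of responders resting on a supported count is not in the documents. The rows below are an assumed range of 0 to 3, not a forecast.

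| Reclassified | Responders | ORR | Lower bound |
|---|---|---|---|
| 0 | 15/24 | 62.5% | 43.7% |
| 1 | 14/24 | 58.3% | 39.7% |
| 2 | 13/24 | 54.2% | 35.8% |
| 3 | 12/24 | 50.0% | 31.9% |

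Each step lowers the bound by about 4 points (43.71 − 39.68 = 4.03; 39.68 − 35.76 = 3.92; 35.76 − 31.94 = 3.82). At 15/24 one patient decides whether the observed ORR lies above the 60% target.

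**3. Who can take this route.** All of the following must hold:
- Group A is met, or platelets or hemoglobin is the only abnormal parameter.
- Neither platelets nor hemoglobin meets its line unaided. One suffices, so a patient with either count above the line already qualifies.
- The count used for response is a supported one.

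**4. How far a platelet transfusion reaches.** Let B be the baseline count and I the transfusion increment. The documents give no increment; assume I = 20,000 to 40,000/µL. The PR line is 1.5B up to B = 100,000/1.5 = 66,667, and above 100,000 beyond that.
- *After an iwCLL grade 4 fall* (at least 75% by Table 12, for baselines below 100,000): the count is at most 0.25B. Reaching the line needs 0.25B + I ≥ 1.5B, so B ≤ I/1.25, which is 16,000 to 32,000. For B above 66,667 it would need I above 100,000 − 0.25B, which is at least 75,000 and outside the assumed range.
- *Transfused while still near baseline*: B + I ≥ 1.5B, so the increment must be at least half the baseline.

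Section 5.1.8 admits platelets below 50,000/µL only with documented marrow involvement, so the very low baselines come in under that exception.

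**5. G-CSF.** Neutrophils are not a PR item. For CR, a supported neutrophil count changes the label between CR and CRi, and Section 9.4.2 counts both. The effect on ORR is 0.

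**6. Baseline.** The 50% line is 1.5 times baseline, and nothing requires the baseline count to be unsupported. A baseline raised by 10,000 raises the line by 15,000 (until the 100,000 alternative applies), which can remove a responder.

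**The case against.** The best defense is that the route is narrow. Supportive care cannot normally make a PR by itself, because two group A improvements are also needed. Either count above its line unaided closes the question. The criteria are silent on supported platelets; they do not expressly accept them. Section 7.5 adopts the 2018 iwCLL definitions by reference, and whether those cover supported counts cannot be checked here. No test or power calculation depends on ORR. All of this stands and limits the size of the point. It does not remove it: the written criteria separate hemoglobin from platelets, and Table 17 separates neither.

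Three stronger readings are tempting but unsupported:
- *That the omission can only add responders.* A transfused baseline can remove one (step 6). Myelosuppression also lowers counts and makes the PR blood-count item harder to meet, and PR has no counterpart to CRi.
- *That G-CSF can create a PR.* It cannot (step 5).
- *That the 2 of 5 patients with grade 4 thrombocytopenia in Section 4.1 show how often this would happen.* After a fall of that depth, a transfusion reaches the PR line only from very low baselines (step 4). Those patients were also on the superseded 3-day schedule, and Section 9.1.1 leaves them out of the analysis.

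**Conclusion.** The point holds as a gap in the response definition that reaches the primary endpoint. The text guards one of two alternative blood-count lines against one form of support, and Table 17 guards neither. A platelet count after transfusion or a hemoglobin on erythropoietin can therefore satisfy the PR requirement.

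The size is known per patient only: 4.2 points of ORR and about 4 points of lower bound at N=24. The number of patients cannot be derived from the documents. For platelets the route mainly concerns very low baselines or patients transfused near their baseline count; that statement rests on the assumed 20,000 to 40,000/µL increment. The consequence is possible bias in the estimate and its bound, not an error in a test. It is worth correcting because the change is small and follows a principle the protocol already applies to hemoglobin.

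**What to change.** - In Section 7.5.2 and Table 17, require that platelet counts used for response be free of platelet transfusion, and hemoglobin free of red cell transfusion and erythropoietin, within a look-back window that the sponsor chooses and pre-specifies.
- Make the matching change in Section 7.5.1, noting that it affects the CR versus CRi label. A G-CSF condition on neutrophils, if wanted, belongs here and does not bear on ORR.
- Apply the same condition to the baseline count. Section 6.7 records transfusions and medications from 28 days before C1D1, whereas screening may run to 42 days. The baseline count should therefore be one whose look-back lies inside the recorded period; hematology is scheduled on C1D1.
- Make Table 17 agree with the text.
- Add a sensitivity ORR that treats supported counts as not meeting the criterion.

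Nothing here changes what support patients receive. The cost is an edit to Section 7.5, a small programming check against data already in the eCRF, and an ORR that may come out slightly lower.

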# 7.5.3 Progressive Disease

Progressive disease during or after therapy is characterized by at least one of the following:

- Lymphadenopathy: Progression of lymphadenopathy as confirmed by physical examination. Disease progression occurs if one of the following events is observed:
  - Appearance of any new lesion, such as enlarged lymph nodes (≥ 1.5 cm), splenomegaly, hepatomegaly, or other organ infiltrates.
  - An increase by 50% or more in greatest determined diameter of any previous site.
- Splenomegaly: An increase in the spleen size by ≥ 50% of the extent of enlargement of the spleen below the costal margin or the de novo appearance of splenomegaly defined by palpation. If no prior splenomegaly was observed at baseline or if splenomegaly has resolved with treatment, the spleen must increase by at least 2 cm from baseline.
- An increase in the liver size of ≥ 50% of the extent enlargement of the liver below the costal margin defined by palpation, or the de novo appearance of hepatomegaly. Given the impact of numerous medical conditions, liver size by physical examination or by CT scan is not a reliable measure of hepatic involvement by CLL and should only be counted if hepatomegaly is clearly attributable to lymphoid involvement.
- An increase in the number of blood lymphocytes by 50% or more with at least 5 x 10^9/L B lymphocytes.
- Transformation to a more aggressive histology (e.g., Richter syndrome or Richter transformation). Whenever possible, this diagnosis should be established by lymph node biopsy.

- Occurrence of cytopenia (neutropenia, anemia, or thrombocytopenia) directly attributable to CLL and unrelated to autoimmune cytopenias.
  - During Therapy: Cytopenias may occur as a side effect of many therapies and should be assessed according to CTCAE criteria. During therapy, cytopenias cannot be used to define disease progression. Dose reductions for cytopenias are outlined in Section 6.
  - After Treatment: The progression of any cytopenia (unrelated to autoimmune cytopenia), as documented by a decrease of Hb levels by ≥ 20 g/L (2 g/dL) or < 100 g/L (10 g/dL), or by a decrease of platelet counts by ≥ 50% or to < 100 x 10^9/L, which occurs at least 3 months after treatment, defines disease progression, if the marrow biopsy demonstrates an infiltrate of clonal CLL cells and is not considered treatment-related toxicity.

